## **Revision History**

Document number	Date	Comments
EX-MKTG-156	02/01/2024	First draft (v 1.0)
EX-MKTG-156	02/06/2024	Final

# **Protocol Synopsis**

Protocol Number	EX-MKTG-156
Title	Clinical Evaluation of Biomedics Monthly sphere and Avaira Vitality sphere
Name of Device(s) and (by USAN material)	Biomedics ® 55 Evolution (ocufilcon D), Avaira Vitality™ (fanfilcon A) Note: Avaira Vitality brand is sold as Liberti™ in Mexico.
Indications for Use	
 
Approved for use:
 
ocufilcon D. (Daily wear)
 
fanficlon A. (Daily wear)
 
Indication for use in this study:
 
15 minutes daily wear
 

Study Design	Single-blind, (participant masked), interventional, prospective, direct refit, bilateral wear study.
Purpose	The aim of this non-dispensing fitting study is to evaluate the short term lens fit, of the Biomedics ® 55 Evolution sphere when compared to the Avaira Vitality ™ sphere lenses after 15 minutes of daily wear each.
Study Duration	
 
The anticipated timeline for this study is as follows:
 
Patient enrolment and completion: March 11 - April 6, 2024 Visits: V1: (BL/trial fit/lens order), V2: Dispense / evaluate P1 V3: 15 minutes. Evaluate P1/Dispense P2. V4: 15 minutes. Evaluate P2 / study exit
 

Patient Population	Adapted soft contact lens wearers that provide written informed consent and meet protocol entry criteria.
Sample Size	Target enrollment and completion is 40 subjects.
Center Destination (Mexico)	Consultorio Optométrico [name]
Number of Centers	Single Center
Primary Endpoint	Lens Fit Acceptance Ratings

### 1 Introduction

According to a recent International survey in 2023 soft contact lenses accounted for 90% of lens fits in 2023 (*Contact Lens Spectrum* market data). There is considerable variation between countries with respect to prescribing by lens material but on average frequent replacement hydrogels were prescribed 7% (range 0% - 36%), while silicone hydrogel lenses were prescribed on average 33% (range 8% - 75%).

As reported in previous years there is a clear trend indicating that silicone hydrogel materials make up most of the fits and refits that are conducted today (Contact Lens Spectrum market data). In the United States silicone hydrogels were reported in usage at 59%, while hydrogels were reportedly used in 29% of fits in 2023. In terms of lens modality, spherical lenses were prescribed 43% of the time.

Therefore, CooperVision is interested in comparing the short-term clinical performance and subjective acceptance of Biomedics® 55 Evolution sphere (**LENS A**), to Avaira VitalityTM sphere (**LENS B**), contact lenses. A non-dispensing fitting study is proposed to evaluate the short-term clinical performance of these lenses.

### 2 Study Objective

The aim of this non-dispensing fitting study is to evaluate the short term lens fit, vision performance and patient subjective experiences of the Biomedics® 55 Evolution sphere when compared to the Avaira Vitality™ sphere after 15 minutes of daily wear each.

### The primary outcome variable is:

• Lens Fit Acceptance ratings (assessed by the investigator)

### 3 Study Hypothesis

### 3.1 Study Hypothesis

- Null hypothesis (Ho): There is no difference in clinical performance and subjective assessments between lens types.
- Alternative hypothesis (H1): There is a difference in clinical performance and subjective assessments between lens types.

### 4 Study Design

This is a **40-subject**, single-blind, (participant masked), interventional, prospective, direct refit, bilateral wear study. It is anticipated that this study will involve 4 visits as follows: **V1:** (BL/trial fit/lens order), **V2:** Dispense / evaluate P1. **V3:** 15 minutes. Evaluate P1/Dispense P2. **V4:** 15 minutes. Evaluate P2 / study exit.

### 5 Investigational Sites

### 5.1 Number of Sites

This will be a single center investigational site in Mexico City. (Target 40 subjects).

### 5.2 Investigator Recruitment

This study will be conducted at the investigator's private practice located at: Consultorio Optométrico [name] The Investigators will be required to fulfil the following criteria:

- Licensed optometrist with at least two years of contact lens fitting experience.
- Experienced Investigators who will be trained in Good Clinical Practice (GCP) by the principal investigator.
- In-office email or fax.
- Willingness to follow the study protocol and to co-operate with the study monitors.

This clinical study is designed to be in conformance with the ethical principles in the Declaration of Helsinki, with the ICH guidelines for Good Clinical Practice (GCP) and all the applicable local guidelines.

### 6 Ethics Review / Statement of Compliance

### 6.1 Relevant Standards / Guidelines

This implementation document has been developed in accordance with the following:

- ISO 14155. Clinical Investigation of Medical Devices
- ICH Harmonized Tripartite Guideline for Good Clinical Practice
- Declaration of Helsinki

### 6.2 Institutional Review Board

This study will be conducted in accordance with Institutional Review Board regulations (U.S. 21CFR Part 56.103) or applicable IEC regulations. Copies of all IRB/IEC correspondence with the investigator/sponsor will be kept on file. The study will commence upon approval from the following Ethics Committee: Comisión de Ética de la FESI. [name],

[name]. [contact] and email address [contact].

### 6.3 Clinical Trial Registration

This study will be registered with clinical trials.gov in accordance with section 801 of the Food and Drug Administration (FDA) Act which mandates the registration of certain clinical trials of drugs and medical devices.

### 6.4 Informed Consent

Informed consent, **sector**, shall be obtained in writing from the subject and the process shall be documented before any procedure specific to the clinical investigation is carried out.

### 7 Potential Risks and Benefits to Human Subjects

There may be direct benefits to the subjects in this study such as improved vision, comfort, convenience, and cosmetic advantage. Participation in a study may contribute to scientific research information that may be used in the development of new contact lens products. In addition, subjects will receive an examination of the front part of their eyes and may have the opportunity to try a different type of soft contact lenses and/or different lens care products at no cost to them. The contact lens materials used in this study are commercially available intended for daily wear (NOT extended wear) similar to the average wearing time of 10-16 hours for daily wear lenses.

This study is considered to be a non-significant risk study based on United State Food and Drug administration (FDA) and International Standards Organization (ISO) guidelines because the study devices used as intended in this study (daily wear) don't represent a potential for serious risk to the health, safety or welfare of the subject, and (2) it is not an implant, (3) it is not used to support or sustain human life, (4) it is not of substantial importance in diagnosing, curing, mitigating or treating disease or otherwise prevents impairment of human health, (5) does not present a potential for serious risk to the health, safety or welfare of the subject.

Complications that may occur during the wearing of contact lenses include discomfort, dryness, aching or itching eyes, excessive tearing, discharge, hyperemia and variable or blurred vision. More serious risks may include photophobia, iritis, corneal edema or eye infection. Although contact lens-related infections are very infrequent, the possibility does exist. The incidence of infection due to day-wear soft lenses is 0.035%. Almost always an infection will occur only in one eye. This risk is assumed by 35-million Americans who currently wear contact lenses.

Routine clinical procedures including auto-refraction, auto-keratometry, visual acuity, anterior ocular health assessment, and contact lens fitting will be used. In addition, high magnification imaging of the lens fit may be made using 35 mm or digital cameras, in vivo confocal microscopy, and/or specular microscopy. Patients will be monitored in the clinic during the study to reduce if not eliminate the occurrence of adverse or potential adverse events. Patients will be given instructions from the study investigator regarding early symptoms and signs of adverse events and their contact information.

### 8.1 Participants

Habitual soft contact lens wearers who currently wear sphere lenses for distance vision correction and provide written informed consent and meet the protocol entrance criteria. Subjects will be recruited from the investigator's private practice databases who agree to voluntarily participate in the study **Example 1**. All subjects will be screened to determine study eligibility. Each subject will be given a unique ID number. Additionally, all subjects must meet the study inclusion and exclusion criteria listed below.

### Inclusion criteria

A person is eligible for inclusion in the study if he/she:

- 1. Is at least 18 years of age and has full legal capacity to volunteer.
- 2. Has read and signed an information consent letter.
- 3. Self-reports having a full eye examination in the previous two years.
- 4. Anticipates being able to wear the study lenses for the required time of the study.
- 5. Is willing and able to follow instructions and maintain the appointment schedule.
- 6. Has refractive astigmatism no higher than -0.75 DC.
- 7. Can be fit with the available lens parameters (sphere +6.00 to -10.00D). See Table 1.
- 8. Can achieve binocular distance vision of at least 20/30 Snellen (logMAR 0.18) with the study contact lenses.

### **Exclusion Criteria**

A person will be excluded from the study if he/she:

- 1. Is participating in any concurrent clinical or research study.
- 2. Has any known active\* ocular disease and/or infection that contraindicates contact lens wear.
- 3. Has a systemic condition that in the opinion of the investigator may affect a study outcome variable.
- 4. Is using any systemic or topical medications that in the opinion of the investigator may affect contact lens wear or a study outcome variable.
- 5. Has known sensitivity to the diagnostic sodium fluorescein used in the study.
- 6. Self-reports as pregnant, lactating or planning a pregnancy at the time of enrolment.
- 7. Has undergone refractive error surgery or intraocular surgery.

\* For the purposes of this study, active ocular disease is defined as infection or inflammation which requires therapeutic treatment. Mild (i.e., not considered clinically relevant) lid abnormalities (blepharitis, meibomian gland dysfunction, papillae), corneal and conjunctival staining and dry eye are not considered active ocular disease. Neovascularization and corneal scars are the result of previous hypoxia, infection or inflammation and are therefore not active.

Pregnant and lactating women are not being excluded from the study due to safety concerns but due to fluctuations in refractive error, accommodation and/ or visual acuity that occur secondary to systemic hormonal changes. It has further been shown that pregnancy could impact tear production, which could impact dry eye symptoms. Such fluctuations could affect data, thereby negatively affecting study data integrity.

### 8.2 Study Materials

### 8.2.1 Contact lens

CooperVision will provide the site with an inventory of both study lenses (LENS A) and (LENS B) to allow participants to be fit with the lens powers available for this study.

All subjects will be trial fitted and, if suitable, dispensed the first pair of the assigned lens brand assigned per a determined table **assigned**. The lenses used in this study are all FDA approved and marketed products. Details of the study contact lenses are shown in Table1.

Brand	Biomedics ® 55 Evolution (LENS A)	Avaira Vitality™ (LENS B)	
Manufacturer	CooperVision Inc.	CooperVision Inc.	
Material	ocufilcon D	fanfilcon A	
WC %	55	55	
Base Curve (mm)	8.6	8.4	
Lens Diameter (mm)	14.2	14.2	
Sphere Power (D)	+ 6.00 to – 10.00 (0.50 steps after ± 6.00)	+ 6.00 to - 10.00 (0.50 steps after ± 6.00)	
Wearing schedule	Daily wear	Daily wear	

### Table1: Study lens parameters

### 8.2.2 Contact Lens care

Since this is a non-dispensing fitting study no contact lens care will be required. However, in the event that the study lenses need to be rinsed during the insertion process, preserved saline solution will be used.

### 8.2.3 Storage of Study Medications/Treatments

There are no unapproved investigational products used in this study requiring special storage accommodations.

### 8.2.4 Clinical Supply Inventory

There are no unapproved investigational products used in this study requiring special inventory requirements.

### 8.2.5 Disposal of Consumables

This study dispenses consumables (lenses) to participants for use during the study. Study lenses worn by participants will be discarded by the principal investigator at the end of the study.

### 8.2.6 Masking and Control of Study Materials

The contact lenses, (LENS A, and LENS B), will be masked to the subject only. The lenses will be removed from their blister pack by an assistant and transferred to an unmarked lens case to maintain the participants masked of the study lenses. Participants will then be instructed to remove the lenses from the lens case and insert them onto their eyes. It is not possible for the study investigators to be masked because of the need to follow the specific lens fitting guide during the lens prescription optimization visit.

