### 8.3 Visit Schedule and Procedures

This will be an interventional, subject masked, bilateral, non-dispensing fitting study. Participants will be examined at two different points over the course of one day, V1 (lens dispensing), V2 (15 minutes post lens settling). Participants will wear two different pairs of lenses with **LENS A** fitted first to all participants, followed by **LENS B**. Anterior ocular health examination will be performed at baseline without the use of fluorescein.

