# The following outline identifies the two study visits and the general procedures, **and a state of the study and recorded in the case report forms**:

### 8.3.1 Visit 1: Baseline / Trial Fit / Lens order

- Subjects should attend this visit wearing their spectacle lenses.
- Explanation of the study.
- Sign informed consent form.
- Collect habitual sphere lens brand information.
  - o Brand
  - Power(s)
  - Replacement schedule (daily, 2-week, monthly)
- Anterior ocular health examination (Slit lamp without fluorescein).
- Insert trial LENS A
- Measure high contrast distance visual acuity and optimize the prescription if needed.
- Evaluate lens fit (
   lens fit acceptance)
- Order final LENS A.
- Remove LENS A and insert trial LENS B.

- Measure high contrast distance visual acuity and optimize the prescription if needed.
- Evaluate lens fit ( lens fit acceptance)
- Order final LENS B.

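### LENS A is worn first by every participant, so the paired comparison cannot separate lens from wearing order; open grading of the primary outcome adds a secondary risk

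*Combined protocol and SAP*

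**What the plan says.** **Outcome and rater.** The only primary outcome named in section 2 is "Lens Fit Acceptance ratings (assessed by the investigator", with no visit attached. The objective compares Biomedics 55 Evolution with the Avaira Vitality "sphere after 15 minutes of daily wear each", which points to the 15-minute grades at Visits 3 and 4 (sections 8.3.3 and 8.3.5). Fit is also graded at Visit 1 (section 8.3.1) and Visit 2 (section 8.3.2).

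**Order.** Section 8.3 has LENS A "fitted first to all participants, followed by" LENS B. The headings of sections 8.3.2 to 8.3.5 follow that order and name the lens. Section 8.2.1 says that the first pair follows a preset assignment table; some text is removed at that point.

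**Masking.** Section 8.2.6 masks the subject only. It says that investigators cannot be masked "because of the need to follow the specific lens fitting guide during the lens prescription optimization visit". In the visible text, optimisation appears at Visit 1: "Measure high contrast distance visual acuity and optimize the prescription if needed". For participant masking, "The lenses will be removed from their blister pack by an assistant and transferred to an unmarked lens case", after which "Participants will then be instructed to remove the lenses from the lens case and insert them onto their eyes".

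**Analysis.** The alternative hypothesis in section 3.1 is "There is a difference in clinical performance and subjective assessments between lens types". Section 10.1 plans paired comparisons of the lenses and mentions no period term. Section 10.2 claims 84% power for a 0.4-point difference with 40 subjects.

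**The concern.** A paired comparison attributes the mean within-subject difference to the lens only if nothing else changes systematically between the two grades. Here LENS A is always the first pair and LENS B always the second. Anything that changes from the first wearing to the second, such as the state of the eye after one lens has been worn or drift in the investigator's grading, enters the mean difference in full. It does not shrink with more subjects.

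The grader's knowledge of the lens adds a second possible contribution. It is weaker as a criticism: it is openly declared, and it is a risk rather than a structural certainty. The two matter together because the study tests for a difference between lens types and is powered for one. Either result, a difference or none, would be hard to attribute to the lens.

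**Working it through.** **Inputs.** From section 10.2: n = 40, SD of paired differences 0.83, two-sided alpha 0.05, design difference 0.4. The bias sizes below are assumptions, because the documents give none.

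**1. The plan's power.** Standard error = 0.83/√40 = 0.1312. Noncentrality = 0.4/0.1312 = 3.048, with 39 df and critical t = 2.023. The noncentral t gives power 0.8443, which matches the 0.844271 in Figure 1. The rows for n = 36 (0.8027) and n = 48 (0.9049) also reproduce. The arithmetic is sound; the issue is bias.

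**2. What the fixed order can estimate.** Let λ be the lens effect (B minus A) and π the order effect (second minus first). In every subject the expected difference is λ + π, so only the sum can be estimated. A model with 40 subject effects, one period term and one lens term has 42 columns but rank 41. With 20 subjects in each order the rank is 42. The second-minus-first difference is then π + λ in the A-B group and π − λ in the B-A group, and half the contrast between the groups is λ.

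An effect of the grader knowing the lens, ρ, belongs to the lens label and gives λ + ρ in either order. Randomising the order therefore does not remove it.

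**3. Effect of a systematic shift.** Noncentrality = shift/0.1312 when there is no true difference, and (0.4 − shift)/0.1312 when the shift opposes a true 0.4.

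| Assumed shift (grade) | False-positive rate, no true difference | Power, true 0.4, shift opposing |
|---|---|---|
| 0 | 5.0% | 84.4% |
| 0.05 | 6.6% | 73.9% |
| 0.10 | 11.5% | 60.6% |
| 0.20 | 31.8% | 31.8% |

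For scale, the smallest observed mean difference that reaches significance is 2.023 × 0.1312 = 0.27 grade. A constant shift is a simplification on a whole-grade scale. If the same mean shift came from one-grade changes in on average 2, 4 or 8 of 40 subjects, the SD would be √(0.83² + s(1 − s)) with s = 0.05, 0.10 or 0.20, and the false-positive rates would be about 6.5%, 10.8% and 26.8%.

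**4. Cost of a balanced order.** With 20 subjects per order and period adjustment, the standard error is ½√(0.83²/20 + 0.83²/20) = 0.1312, as before. Degrees of freedom fall to 38, and power for 0.4 is 0.8438, or 84.4%. In simulation the false-positive rate stayed between 0.049 and 0.052 for order effects from 0 to 0.4. If the order were balanced but ignored in the analysis, power would be about 84.1% or 83% for an order effect of 0.10 or 0.20.

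**The case against.** The strongest defence is that this is a declared design. The Synopsis and section 4 describe a single-blind, participant-masked, direct refit study, section 8.2.6 says that investigators are not masked, and section 8.3 states the order. No document shows an order effect or a grader who favours a lens, and the shifts above are assumed. All of this stands as to size and direction. It does not restore identifiability: disclosing the order does not let the data separate it from the lens.

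A reader might infer that the reason in section 8.2.6 is simply wrong for Visits 3 and 4. The documents do not support that. The headings of Visits 2 and 3a both refer to fitting a lens, and the Visit 2–4 outlines are incomplete as read, so later fitting steps cannot be excluded. The same person may also fit and grade; the documents do not say. What stands is that the stated reason does not clearly reach the 15-minute grades.

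A reader might also infer that masking the grader would clearly work. It may fail: the investigator fits both lenses at Visit 1, and the base curves differ (8.6 and 8.4 mm, section 8.2.1). The assistant's role is described only for participant masking.

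Finally, the preset table in section 8.2.1 might mean that the order varies. Section 8.3 and the visit headings say otherwise, so this is an inconsistency to reconcile rather than a safeguard.

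**Conclusion.** The point holds, led by order. Under section 8.3 lens and wearing order are completely aliased, and no analysis of the planned data can attribute a difference in fit grade, or its absence, to the lens alone. This rests on section 8.3 governing over the table in section 8.2.1.

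Open grading is a secondary risk of unknown size and direction. Both lenses come from the same manufacturer and the hypothesis favours neither, so a bias towards one lens should not be inferred.

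The magnitudes are illustrations. A shift of 0.05 matters little for false positives (6.6%); 0.20, half the design difference, would raise them to 31.8%. Treating the Visit 3 and 4 grades as primary is an inference from the objective. The proposed order also assumes that any carry-over from the first pair is the same in both orders. It is a low-cost change that should be made.

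**What to change.** 1. **Order and analysis.** In section 8.3, replace the fixed order at Visits 2–4 with a balanced randomised A-B / B-A order, about half the subjects in each. Make section 8.2.1 consistent with it and add a period term to the paired analysis in section 10.1.
2. **Primary time point.** In section 2, state that the 15-minute grades at Visits 3 and 4 are the primary grades.
3. **Secondary step: attempted masking.** Have the existing assistant present each pair at Visits 2–4 in a coded, unmarked case. Use *first pair* and *second pair* in the visit and form titles. Release the code after the data freeze mentioned in section 11.1, or earlier if a subject's safety requires it. Report this as attempted investigator masking only. If adopted, amend the Synopsis, section 4 and section 8.2.6 to match.
4. **If the fixed order is kept.** State in the protocol that a lens difference cannot be separated from wearing order or from open grading, and limit the conclusion accordingly.

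**Cost.** A randomisation list for 40 to 44 subjects and changes to the forms and the sections named. No added visits, staff or measurements, and almost no loss of power. Grader masking may be incomplete; even then, the randomised order separates order from lens.

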### 8.2.7 Ordering and Accountability of Study Materials

The study sponsor will supply the investigators with the study lenses to use during the study.

